# 1. SYNOPSIS

Study Title	Multi-centre EuRopean study of MAjor Infectious Disease Syndromes (MERMAIDS): Acute Respiratory Infections in Adults	
Ref. no. / short title	MERMAIDS – ARI	
Study Design	Prospective, observational study	
Study Participants	Adults (≥ 18 years old) with a suspected community acquired acute respiratory tract infection, Group 1: attending primary care Group 2: admitted to hospital	
Planned Sample Size	Primary Care patients (Group 1): n = 750 Hospitalised Patients (Group 2): n = 2,250	
Planned Study Period	60 months	

	Objectives	Outcome measures
Primary objective	Identify host and pathogen related determinants of severity of community acquired acute respiratory infections (ARI) in adults.	Differentially expressed host genes (≥ 2- fold difference in expression levels) as assessed by RNA transcriptome microarray in hospitalised and primary care managed cases of ARI, stratified by pathogen* and comorbidity**. *Influenza virus, Human Rhinovirus, Respiratory Syncytial Virus, Streptococcus pneumoniae ; **No comorbidity, chronic pulmonary disease, chronic cardiovascular disease, chronic metabolic disease (diabetes)
Secondary objectives	Describe the aetiology, clinical management and outcomes of adult patients with community acquired ARI, in both primary care and hospital care, across Europe.	
 
In both groups:
 
Prevalence of detection of putative pathogens in respiratory tract samples
 
Proportion of cases receiving antibiotics, antivirals, antifungals and/or immunomodulators.
 
28 day mortality
 
Additional in group 1 (primary care):
 
Proportion of cases requiring hospitalisation
 

	Objectives	Outcome measures
		
 
Additional in group 2 (hospitalised patients):
 
Severity of illness at enrolment as assessed by Pneumonia Severity Index (PSI) and CURB-65
 
Proportion of cases requiring during
 

		admission: supplemental oxygen; non- invasive or invasive mechanical ventilation; extra-corporeal life support.
		
 
Duration of invasive mechanical ventilation and extra-corporeal life support, if applicable
 

		
 
Proportion of cases requiring Intensive Care Unit (ICU)/High Care Unit (HCU) admission
 

		Hospital - and ICU/HCU length of stay
		In-hospital mortality

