# 3.3 Rationale for study design

While experimental research remains essential to provide the foundations of our understanding of disease pathogenesis, detailed patient-oriented studies across the spectrum of clinical disease and aetiologies are needed to understand the complexities of 'real-life' pathogenesis of human infection, including the combined complex influences of age, comorbidities and co-infections with other pathogens in development of severe disease. This approach requires adequately sized and well defined cohorts with regards to age, presence of comorbidities and microbial aetiologies. To date, such patientoriented research in ARI has been limited to relatively small and heterogeneous groups of patients, in which data from patients of different ages with a diverse spectrum of comorbidities were usually combined (9–11). This makes identification of clinical background- or pathogen-specific pathophysiological pathways problematic if not impossible. In addition, most studies to date have focused on the severe end of the clinical spectrum (11-13). Although there are many genes that have increased expression regardless of the pathogen (14,15) differences are generally observed if the samples are taken early enough in the disease (16). There is also limited data on primary care patients and outpatients. Finally, many studies have investigated a single time point (11,13,17–21); analysing more time points is required to fully understand the dynamic nature of the host transcriptional profile (7).

Therefore, given the heterogeneity of clinical backgrounds and causative pathogens, the generation of meaningful insights into the relative contributions of host and pathogen factors to severe disease will require adequately sized cohorts of ARI patients across disease severities. The aim of the MERMAIDS ARI study is to establish such a cohort by enrolling sufficient numbers of patients across the most prevalent comorbidities (chronic pulmonary/cardiovascular/metabolic disease) and most prevalent pathogens (Influenza A, HRV, RSV and *Streptococcus pneumoniae*) with mild (community care) or moderately severe (hospitalised) ARI to have adequate statistical power to analyse differences in host response between these predefined subgroups. A small subset of ARI patients will progress to severe disease, as defined by the need for mechanical ventilation and/or death.

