# 7.7 Clinical parameters

#### 7.7.1 From all subjects

- Patient demographics and medical history, at enrolment
- Description of clinical signs and symptoms, in the 14 days before enrolment and at enrolment (Day 0)
- Physical examination, at enrolment (including respiratory rate and oximetry see CRF for complete list)
- Discharge/final diagnosis as determined by attending physician
- Presence of febrile illness at day 28
- Mortality at day 28

#### 7.7.2 Additional clinical parameters from Group 1

- in the 14 days before enrolment to day 28:
  - All relevant laboratory results as ordered by routine care
  - All relevant prescribed medication (e.g. antivirals, antibiotics, antifungals, antiinflammatory drugs, steroids, other immune modulators, statins, ACEinhibitors/angiotensin receptor blockers).
  - Results of all relevant microbiological testing as ordered for routine care

- Percentage of patients admitted to hospital by day 28

#### 7.7.3 Additional clinical parameters from Group 2

- Pneumonia Severity Index (PSI) at admission
- CURB-65 severity score, at enrolment
- Requirement of (at any time during admission):
  - supplemental oxygen
  - non-invasive mechanical ventilation
  - invasive mechanical ventilation
  - extra-corporeal life support
- If applicable, duration of invasive mechanical ventilation and extra-corporeal life support
- In the 14 days before admission to day 28:
  - All relevant laboratory results as ordered by routine care
  - All relevant prescribed medication (e.g. antivirals, antibiotics, antifungals, antiinflammatory drugs, steroids, other immune modulators, statins, ACEinhibitors/angiotensin receptor blockers).
  - Results of all relevant microbiological testing as ordered for routine care
- Date of hospital admission and discharge, transfer or death
- Date of high care unit/intensive care unit admission and discharge, transfer or death, if applicable
- Clinical outcome: hospital discharge, transfer or in-hospital death

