#### 8.5 Statistical analysis of secondary outcome measures

Statistical analysis of secondary endpoints will be descriptive in nature and include estimates of rates and proportions. Hypothesis testing is not envisaged to be a part of the statistical analysis of secondary endpoints.

All participants with evaluable samples and informed consent will be included in the analysis.

Proportions will be estimated for the prevalence of each pathogen in respiratory tract samples; the proportion of cases receiving antibiotics, antivirals, antifungals and/or immunomodulators; and proportion not surviving to 28 days post enrolment. Estimates will be presented for primary and hospital care groups separately, with 95% confidence intervals estimated using the binomial exact method. Additional binary endpoints will be analysed in the same manner.

Time to event variables such as time to discharge (length of stay) or time on ventilation will be described using the Kaplan-Meier method.

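### Section 8.5 names Kaplan-Meier for time to discharge and time on ventilation without saying how deaths are handled; if they are censored, the curve overstates how many patients leave alive, and how soon.

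*Protocol*

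**What the plan says.** Protocol section 8.5 fixes the estimator for durations: "Time to event variables such as time to discharge (length of stay) or time on ventilation will be described using the Kaplan-Meier method". The section says nothing about what counts as the event, what is censored, or how a death in hospital or on support enters the curve. It also says that the secondary analyses are descriptive and that no hypothesis tests are planned.

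The durations concerned are secondary outcomes for the hospitalised group ("Hospitalised Patients (Group 2): n = 2,250"). The synopsis lists "Hospital - and ICU/HCU length of stay", and section 7.7.3 lists "If applicable, duration of invasive mechanical ventilation and extra-corporeal life support".

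Section 7.7.3 keeps the possible ends of a stay apart. It records "Clinical outcome: hospital discharge, transfer or in-hospital death", with "Date of hospital admission and discharge, transfer or death", and for intensive or high care "Date of high care unit/intensive care unit admission and discharge, transfer or death, if applicable". Section 3.3 links ventilation and death: "A small subset of ARI patients will progress to severe disease, as defined by the need for mechanical ventilation and/or death". In-hospital and 28-day mortality are separate secondary outcomes, reported as proportions.

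**The concern.** A patient who dies in hospital can no longer be discharged, and one who dies on a ventilator can no longer come off it alive. Death is a competing event for both.

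Kaplan-Meier handles one type of event plus independent censoring. If discharge is the event and deaths are censored, the estimate treats each patient who died as if still at risk and leaving alive at the rate of those who remain. Some of the dead are thus counted as future discharges. If death is counted as the event instead, the curve is sound for time to any exit, but it puts deaths and recoveries together.

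At stake is the meaning of the published curves and medians. A reader who sees a time-to-discharge curve will take its complement as the proportion who have gone home, and under neither handling of death is that what it shows. The gap grows with mortality, so it would be larger for ventilation and extra-corporeal support than for hospital stay as a whole.

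**Working it through.** **No figure to reproduce.** The protocol gives no estimate, precision or sample size for length of stay or time on ventilation.

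**Inputs.** The estimator is from section 8.5, the separate ends of stay from section 7.7.3, and the day-28 horizon from the follow-up schedule. Mortality and duration are not in the documents. The values below are assumptions, shown as a range.

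**Formulas.** Let exits of any kind occur at a constant hazard h = ln 2 / (median time to any exit), and let a share d of exits be deaths.
- Kaplan-Meier with deaths censored: 1 − KM(t) = 1 − exp(−h(1−d)t).
- True cumulative incidence of leaving alive: (1−d)(1 − exp(−ht)).
- Kaplan-Meier with death counted as an exit: 1 − exp(−ht).
- Median with deaths censored: (median exit)/(1−d).
- True time by which half have left alive: −ln(1 − 0.5/(1−d))/h.

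**Hospital stay, median exit 7 days.** h = 0.6931/7 = 0.0990 and 28h = 2.773, so exp(−28h) = 0.0625.
- At d = 0.10, censored: 1 − exp(−2.773 × 0.90) = 1 − exp(−2.495) = 0.918.
- At d = 0.10, true: 0.90 × 0.9375 = 0.844.

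| Deaths (assumed) | 1 − KM at day 28, deaths censored | True, discharged alive | Gap (points) | Median, KM v true (days) |
|---|---|---|---|---|
| 2% | 93.4% | 91.9% | 1.5 | 7.1 v 7.2 |
| 5% | 92.8% | 89.1% | 3.8 | 7.4 v 7.6 |
| 10% | 91.8% | 84.4% | 7.4 | 7.8 v 8.2 |
| 15% | 90.5% | 79.7% | 10.8 | 8.2 v 9.0 |

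(Gaps are taken before rounding.)

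**Ventilation, median exit 10 days.** h = 0.0693 and 28h = 1.941, so exp(−28h) = 0.1436.
- At d = 0.30, censored: 1 − exp(−1.941 × 0.70) = 1 − exp(−1.359) = 0.743.
- At d = 0.30, true: 0.70 × 0.8564 = 0.599.
- Medians at d = 0.30: 10/0.70 = 14.3 days with deaths censored; −ln(1 − 0.5/0.70)/0.0693 = 18.1 days true.

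| Deaths (assumed) | 1 − KM at day 28, deaths censored | True, off support alive | Gap (points) | Median, KM v true (days) |
|---|---|---|---|---|
| 20% | 78.8% | 68.5% | 10.3 | 12.5 v 14.2 |
| 30% | 74.3% | 59.9% | 14.4 | 14.3 v 18.1 |
| 40% | 68.8% | 51.4% | 17.4 | 16.7 v 25.9 |

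**Death counted as an exit.** The curve then reads 93.8% by day 28 for hospital stay and 85.6% for ventilation, whatever the death share. Both are right for any exit. Read as leaving alive, they are further off than the censored version: 93.8% against 84.4% at 10% hospital deaths, and 85.6% against 59.9% at 30% deaths on ventilation.

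**Sensitivity to the assumed durations.** With mean exit times of 8 days (hospital) and 10 days (ventilation) in place of the medians above, the day-28 gap is 1.7 to 12.5 points for hospital stay (2% to 15% deaths) and 14 to 28 points for ventilation (20% to 50% deaths).

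**Sensitivity to constant hazards.** A lognormal simulation gave the same direction: about 95% to 97% against 88% at 10% deaths, and about 73% to 83% against 55% to 56% at 40% deaths.

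**The case against.** The strongest reply is that the protocol never says deaths are censored. The outcomes are listed as durations, none is qualified as alive, and section 8.5 equates time to discharge with length of stay. A duration can end at any exit, and Kaplan-Meier is then a valid description. This stands as a limit on the claim. A reader might infer that the plan commits to a biased estimate; the text does not support that. It supports only that the handling of death is unstated and that each of the two ordinary choices misleads if read as time to leaving alive. Nor is this simply detail left to an analysis plan: the protocol has already named the estimator, and calling the variable time to discharge makes discharge the natural event.

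Second, mortality is reported separately, so a reader can set the curve beside it. That softens a misreading but does not correct the curve or its median.

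Third, importance. A reader might infer that comparisons between countries or pathogens would be distorted. Section 3.5 does speak of comparing outcomes across Europe, but section 8.5 specifies estimates only by care group and plans no country- or pathogen-specific stay curves. Nor do the documents make ventilated patients the group of most interest: the primary contrast is hospitalised against primary care patients, and section 3.3 calls severe disease a small subset.

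Fourth, mortality may be low. Section 6.5 excludes patients lacking capacity at entry, and section 11.7 expects 2–5% of hospitalised participants to lose capacity later (45 to 113 of 2,250). This does not fix mortality, but it makes the low-mortality rows for hospital stay more plausible, and there the gap is only 1.5 to 4 points.

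**Conclusion.** The point holds in a limited form. Section 8.5 names an estimator that does not separate death from discharge, for outcomes whose possible ends section 7.7.3 does separate, and it leaves the handling of death open. With deaths censored, the direction of error is certain: one minus Kaplan-Meier is never below the cumulative incidence of leaving alive and exceeds it once deaths have occurred.

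The size is not certain, because every mortality and duration figure is assumed. Under constant hazards the day-28 overstatement is about 4 points for hospital discharge at 5% deaths, 7 at 10%, and 14 for ventilation at 30%, where the median is also about 4 days too short (14.3 against 18.1).

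The effect is confined to descriptive secondary outcomes and is small for hospital stay if mortality is low. The primary gene-expression analysis and the sample size are untouched. It is worth correcting because a better estimator is readily available, but it does not threaten the study's main conclusions.

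**What to change.** In section 8.5, replace Kaplan-Meier with Aalen-Johansen cumulative incidence curves, with death as a competing event: discharge alive for hospital stay and for ICU/HCU stay, and end of support alive for invasive ventilation and extra-corporeal life support. State the remaining rules in the same place:
- treat transfer as a separate exit, or state and justify censoring it, since it may not be independent of prognosis;
- censor patients still in hospital or on support at the end of follow-up.

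If time to any exit is what is meant, Kaplan-Meier can stay, provided that the outcome is labelled as time to any exit and shown beside the corresponding mortality.

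The cost is a short amendment to section 8.5 and slightly more analysis work. Section 7.7.3 already provides for the dates and outcomes of hospital stay and the dates of ICU/HCU stay. For ventilation and extra-corporeal support it lists only a duration, so vital status at the end of support may have to be derived from that duration and the date of death.

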# 9. DATA MANAGEMENT

#### 9.1 Source data

Source documents are original documents, data, and records from which participants' CRF data are obtained. These include, but are not limited to, general practice and hospital medical records.

CRF entries will be considered source data if the CRF is the site of the original recording (e.g. there is no other written or electronic record of data). In this study the CRF will be used as the source document for the documentation of inclusion and exclusion criteria, and baseline assessment information, which will include, but not be limited to, comorbidities and severity of symptoms.

All documents will be stored safely in confidential conditions. On all study-specific documents, other than the signed consent and contact details form, the participant will be referred to by the study participant ID, not by name, including on all laboratory results.

#### 9.2 Access to data

Direct access will be granted to authorised representatives from the Sponsor, host institution and the regulatory authorities to permit study related monitoring, audits and inspections.

#### 9.3 Data recording and record keeping

Research Online (RO) is an electronic data capture (EDC) system that will be used for data collection. Web-based case report forms (eCRF) are implemented into the system to facilitate the study specific data collection. These forms can easily be accessed by all standard web browsers. Multiple validation and range checks will be programmed in the eCRF to assure complete and high quality data. Data that does not comply with these rules or ranges will generate a query that must be resolved immediately or at a later stage. Electronic workflows as multiple skip and jump rules will ensure that only information that is applicable to the patient will appear. After the data of last subject is entered, the database can rapidly be closed and data made available for further analysis and publication purposes. This data will not contain any patient identifiable information.

PREPARE | Multi-centre EuRopean study of MAjor Infectious Disease Syndromes

RO meets all requirements according to ICH-GCP standards for electronic data entry with respect to safeguarding data integrity and data security regulations. Users will have role based access to the system logging in using their personal username and password. The system will log all data entry steps with timestamps and user information. The role based access to the system will avoid unauthorised data access and prevents users from performing actions that they do not have authorisation for.

Project management of the study is facilitated by the integrated real live study progress reports. RO data traffic over the internet is encrypted using secured data communication protocols. Dedicated databases and web servers are hosted in a secure data centre, the database (PostgreSQL) is backed up on a daily basis.

The participants will be identified by a unique study specific number and/or code in any database. The name and any other identifying detail will not be included in any study data electronic file.

## 9.4 Standard procedures

To assure high quality the data management (DM) department of the Julius Centre (JC), Utrecht, who will be responsible for the data management within the trial, works according to a Quality Management System. All work is carried out in accordance with our written Standard Operating Procedures (SOP) and Work instructions (WI).

# 10. QUALITY ASSURANCE PROCEDURES

The study will be conducted in accordance with the current approved protocol, GCP, relevant regulations and MERMAIDS Standard Operating Procedures. The monitoring will be performed by the MERMAIDS Study Manager or delegate; these tasks may be delegated to a qualified Organisation. The level of monitoring required will be informed by a risk assessment. All investigators and study related site staff will receive training in study procedures and GCP. Regular study monitoring will be conducted as below to ensure that the rights and wellbeing of human participants are protected during the course of the study and that the data collected is credible and accurate.

Governance of the study will be through the Study Steering Committee (SSC) and the Study Operation Group (SOG).

The SSC will be the primary decision making body, with membership from partner institutions, a senior representative from each participating country, and other independent experts. Decisions of the Committee will be by consensus. Terms of reference for the SSC will set out the full details of the membership, operations and remit.

The SOG will be led from the MERMAIDS Coordination Centre in Oxford and will report to the SSC. The SOG team will provide operational oversight and day-to-day management of the study to ensure compliance to follow up and critical factors such a retention and data quality. The team will comprise those with responsibility for the operational activities and so include study operations, data management and central laboratory.

# 11. ETHICAL AND REGULATORY CONSIDERATIONS

# 11.1 Declaration of Helsinki

The Investigator will ensure that this study is conducted in accordance with the principles of the Declaration of Helsinki (64th WMA General Assembly, Fortaleza, Brazil, October 2013).

# **11.2 Guidelines for good clinical practice**

The Investigators will ensure that this study is conducted in accordance with relevant regulations and with Good Clinical Practice.

# 11.3 Approvals

The protocol, informed consent form, participant information sheet and any proposed advertising material will be submitted to an appropriate Research Ethics Committee (REC), and host institution(s) for written approval. This will be done in collaboration with Work Package 1 of the PREPARE Programme to ensure that the correct regulatory approvals are gained in each participating country.

The Investigator will submit and, where necessary, obtain approval from the above parties for all substantial amendments to the original approved documents.

# 11.4 Reporting

The CI shall submit once a year throughout the study, or on request, an Annual Progress report to the REC Committee, host organisation and Sponsor. In addition, an End of Study notification and final report will be submitted to the same parties.

# **11.5 Participant confidentiality**

The study staff will ensure that the participants' anonymity is maintained. The participants will be identified only by a study ID number on the CRF and any electronic database. All documents will be stored securely and only accessible by study staff and authorised personnel. The study will comply with the Data Protection Act, which requires data to be anonymised as soon as it is practical to do so.

# 11.6 Expenses and benefits

Participants will be reimbursed for their time and travel expenses for all study visits in additional to normal care. This reimbursement will be made in the form of gift card(s) or voucher(s) given once the day 28 visit has been completed. No cash payments will be made. The maximum total reimbursement per participant for all study visits will be 70 Euros (or equivalent in a different currency).

